4.2.3 Other safety endpoints

4.2.3.1 Physical examinations

A complete physical examination is performed at each visit.

Statistical Analysis Plan

Study Name: IFN-K-002

SAP version & date: v4, 18/Jun/2018

The complete physical examination comprises measurements of oral body temperature (in °C), weight, height (Visit 1 only), and routine medical examination of body systems (constitutional, mucocutaneous, neuropsychiatric, musculoskeletal, cardiorespiratory, gastrointestinal, ophthalmic, renal or other).

Safety will be based on abnormalities (normal, Abnormal CS/N, Abnormal CS/AE, Abnormal NCS) in the body systems and raw value for height, weight and body temperature.

4.2.3.2 Vital signs

Vital signs are evaluated during each visit. Vital signs include brachial pulse rate and systolic and diastolic blood pressures. These recordings are made after at least 3 minutes of rest, measured in the supine position. Recordings are made prior to and 1-hour post study product administration, when applicable.

Safety will be based at each visit on raw value and change from baseline.

4.2.3.3 Electrocardiograms (ECG)

Standard 12-lead ECG recordings are made during the Screening Visit, Visit 2 (Week 0), Visit 6 (Week 12), Visit 9 (Week 24) and Visit 12 (Week 36).

Safety will be based on abnormalities (normal, Abnormal CS/N, Abnormal CS/AE, Abnormal NCS).

4.2.3.4 Concomitant medications

Safety will also be assessed based on the analysis of Concomitant medications coded according to the version WHO-DDE 1Q2015 of the WHO-Drug dictionary.

Medication are considered as concomitant if their start date \geq date of first administration or if ongoing at the time of the first administration.

All others will be considered "Prior".

5 Statistical and Analytical Methods

5.1 General considerations

The statistical analyses are performed in accordance with the ICH E9 guideline and will be based on the pooled data from the individual study sites, unless otherwise stated.

The statistical analyses will be performed by an external Contract Research Organization (CRO), Venn Life Sciences, under the responsibility of the Sponsor.

5.1.1 Presentation of results

The following descriptive statistics will be presented:

- For quantitative variables: number of available values, number of missing values, mean, standard deviation, median, Q1 (or first quartiles), Q3 (third quartiles), minimum, maximum values. When

Statistical Analysis Plan

Study Name: IFN-K-002

SAP version & date: v4, 18/Jun/2018

relevant, confidence intervals will be calculated for the mean (Student CI) or the median (Hahn & Meeker 1991).

- For qualitative variables: number of available values, number of missing values, number and percentage of observations in each category of the variable. Except if otherwise specified, percentages will be calculated using the number of available values as denominator (i.e., not including missing values). When relevant, confidence intervals of proportions will be calculated using the Wald method or Clopper-Pearson if Wald is not applicable.

5.1.2 Significance testing and estimation

Two-sided 95% CIs for two-sample differences in means/proportions between the treated and control groups and one-sample means/proportions will be calculated using:

- The normal-approximation method for GMT and other continuous endpoints,
- The “score” method without the continuity correction (Newcombe, 1998a) for binary endpoints.

Unless specified otherwise in the SAP, statistical tests will be two-sided at a 5% significance level.

5.2 Planned analysis

The lists of statistical Tables, Figures and Listings are provided in Section 10.

5.2.1 Demographics and baseline characteristics

The following demographics variables will be summarized by treatment group on the SAF and then in the FAS, if the two analysis sets are different. (Statistical table 14.1.4):

- Age (continuous and class [18-40], [41-65])
- Gender
- Ethnic origin (see section 9 Derived data)
- Presence or absence of renal BILAG at screening
- With or without CS treatment at randomization
- With or without HCQ treatment at randomization
- With or without MMF treatment at randomization
- With or without MTX treatment at randomization
- With or without AZA treatment at randomization

The following baseline characteristics will be summarized by treatment group on the FAS set:

- Alcohol, drug and tobacco use (Statistical table 14.1.5)
- Vital signs at baseline (Statistical table 14.1.6)
- ECG at baseline (Statistical table 14.1.7)
- Physical examination (including Weight, Height and BMI) at baseline (Statistical table 14.1.8)

Statistical Analysis Plan

Study Name: IFN-K-002

SAP version & date: v4, 18/Jun/2018

- Laboratory test: Haematology (Statistical table 14.1.9), clinical chemistry (Statistical table 14.1.10), Coagulation (Statistical table 14.1.11) and Urinalysis (Statistical table 14.1.12) at baseline
- Laboratory test abnormalities (grade or normal, Abnormal CS/N, Abnormal CS/AE, Abnormal NCS): Haematology abnormalities (Statistical table 14.1.13), Chemistry abnormalities (Statistical table 14.1.14), Coagulation abnormalities (Statistical table 14.1.15) and Urinalysis abnormalities (Statistical table 14.1.16) at baseline
- Viral serology, autoantibodies and inflammatory markers at baseline
- Gynecological examination (Cytological examination and HPV on PAP smear) (Statistical table 14.1.20)
- Efficacy variable at baseline (IFN score, SLEDAI-2K score, BILAG global score, SELENA-SLEDAI flare index, CLASI, SLICC/ACR-DI, PGA score, 28-Tender and Swollen Joint Counts, Joint Pain VAS, SF-36 (Physical Component Summary (PCS) and Mental Component Summary (MCS) scores), FACIT (Statistical table 14.1.21)

All demographics data, Alcohol, drug and tobacco use data and gynecological examination data of each patient will be reported in listing 16.2.4.1, 16.2.4.2 and 16.2.4.3 respectively.

Viral serology and pregnancy test data will be listed in Listing 16.2.4.10 and 16.2.4.11.

The definition of baseline is provided in section 5.4.1.

5.2.2 Patient disposition and study discontinuations

Patient disposition will be described (Statistical table 14.1.1). The following variables will be tabulated:

- Number of patients screened
- Number of randomized patients, total and per treatment group
- Number of randomized patient by visit, total and per treatment group
- Number of randomized patients who completed the study as planned (until V12), total and by treatment group
- Number of randomized patients who prematurely discontinued the study (before V12), total and by treatment group
- Reasons for study discontinuations, total and by treatment group

Patient disposition information will be provided in Listing 16.2.1.1. Screen failure will be included in this listing. The reason of screen failure will be presented.

Inclusion and exclusion criteria will be listed in Listings 16.2.1.2 and 16.2.1.3.

The numbers of patient within each dataset (SAF, FAS, PP), globally and by treatment group, will be provided (Statistical table 14.1.2.1, Listing 16.2.3.1) along with reasons for exclusion from the FAS and PP populations (Statistical table 14.1.2.2 and 14.1.2.3 respectively). Reasons for exclusion from the FAS and PP populations will also be provided in Listing 16.2.3.2, according to ICH E3.

All protocol deviations classified during the blinded data review meeting according to definitions provided in section 3.1.1 (Major deviations) and 3.1.2 (Minor deviations) will be tabulated by treatment group for

Statistical Analysis Plan

Study Name: IFN-K-002

SAP version & date: v4, 18/Jun/2018

the FAS population (Statistical table 14.1.3). All major and minor protocol deviations will also be provided in Listing 16.2.2, according to ICHE3.

5.2.3 Medical history – Previous medications

Time since diagnosis (year) and ACR criteria will be presented for SLE medical history (Statistical table 14.1.22 and Listing 16.2.4.4).

SLE flare history will be presented by body system (Statistical table 14.1.23 and Listing 16.2.4.5)

General Medical & Surgical history will be presented by SOC & PT by treatment group (Statistical table 14.1.24).

Medical and Surgical history for each patient will be reported in Listing 16.2.4.6.

Permitted, Prohibited and Previous medications will be presented by ATC code and Preferred Name by treatment group (Statistical tables 14.1.25 to 14.1.27).

Permitted and Prohibited medications for each patient will be reported in Listings 16.2.4.7 and 16.2.4.8.

5.2.4 Efficacy analyses

5.2.4.1 Primary efficacy analysis

Descriptive statistics for IFN gene signature (first co-primary endpoint) at each visit and % of change from baseline by treatment group will be presented (Statistical tables 14.2.1.1.1 and 14.1.1.2).

The first co-primary efficacy endpoint - Percent of change from baseline after 36 weeks of treatment in the expression of IFN-induced genes – will be analyzed using an ANCOVA model (Statistical table 14.2.1.1.3).

The dependent variable will be the percentage of change from baseline in the expression of IFN-induced genes with the treatment as independent variable. The minimization factors used for randomization – Ethnic origin (see section 9 Derived data), Age group, Presence or absence of renal involvement according to BILAG at screening, corticosteroid treatment, hydroxychloroquine treatment and MMF treatment at screening - will be included as covariates. See section 5.3.2 for handling of missing data.

All IFN gene signature data will be listed in Listing 16.2.6.1.1.

Descriptive statistics for the response to treatment according to BICLA (second co-primary efficacy endpoint) at Week 36 will be presented by treatment group (Statistical table 14.2.1.2.1)

The second co-primary efficacy endpoint - response to treatment according to BICLA - will be analyzed using a logistic regression with the response rate as dependent variable and treatment as independent variable, while adjusting for the minimization factors used for randomization, as listed for the analysis of the first primary end-point (Statistical table 14.2.1.2.2).

Statistical Analysis Plan

Study Name: IFN-K-002

SAP version & date: v4, 18/Jun/2018

Response to treatment according to BICLA will be listed in Listing 16.2.6.1.2

First, the hypothesis with respect to the change from baseline in the expression of IFN-induced genes will be tested at an error probability of 5% for a 2-sided test. If and only if this Null-hypothesis can be rejected, the hypothesis with respect to the response to treatment according to BICLA will be tested also at an error probability of 5% for a 2-sided test.

The study will be considered as positive if a statistically significant better effect of IFN-K compared to placebo is observed on the neutralization of the IFN gene signature (i.e. the first co-primary endpoint) and if at least a trend favoring IFN-K is observed on the BICLA response (i.e. the second co-primary endpoint). An observed 10% difference will be considered a marginal effect and a 15% difference will be considered as an important effect, whatever the statistical significance observed.

The primary efficacy analysis will be performed on the FAS set.

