7.1 Screening Period (from Study Week -4 to 0)

Patient eligibility will be determined over the course of the Screening Period.

In order to determine their eligibility, candidate participants will undergo a series of assessments and procedures as outlined in Table 1 and in Section 10.9.1. All relevant samples should be collected before any new SLE related treatment is initiated.

Randomization will be minimized according to the criteria described in Section 9.2.2.

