9.2.2 Randomization of Patients

Treatment allocation at each site will be performed using central randomization via an Interactive Web Response System (IWRS). The randomization algorithm was developed using a stochastic minimization with a minimization probability parameter of 0.80. Randomization will be minimized by:

- Ethnic Origin: Black, Asian, Caucasian/Hispanic, other
- Age: 18-40 & 41-65 years old
- Presence or absence of renal BILAG at screening
- With or without CS treatment at randomization
- With or without HCQ treatment at randomization
- With or without MMF treatment at randomization

At the time of randomization, the IWRS will assign the patient to a treatment arm and will provide the number of the treatment kit for the first injection. The actual treatment numbers administered to the patient will be recorded in the eCRF.

Please refer to Section 10.1 for details about patient identification.

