13.9.2 Analysis of the Primary Efficacy Endpoint

The first co-primary efficacy endpoint - Percent change from baseline after 36 weeks of treatment in the expression of IFN-induced genes – will be analyzed using an ANCOVA.

The dependent variable will be the percentage change in the expression of IFN-induced genes and the treatment as independent variable. The minimization factors used for randomization - Race, Age range, Presence or absence of renal BILAG at screening, corticosteroid treatment, hydroxychloroquine treatment and MMF treatment at randomization - will be included as covariates.

The second co-primary efficacy endpoint - response to treatment according to BICLA - will be analyzed using a logistic regression using the response rate as dependent variable and treatment as independent variable, while adjusting for the minimization factors used for randomization.

First, the hypothesis with respect to the change from baseline in the expression of IFN-induced genes will be tested at an error probability of 5% for a 2-sided test. If and only if this Null-hypothesis can be rejected, the hypothesis with respect to the response to treatment according to BICLA will be tested also at an error probability of 5% for a 2-sided test.

The study will be considered as positive if a statistically significant better effect of IFN-K compared to placebo is observed on the neutralization of the IFN gene signature (i.e. the first co-primary endpoint) and if at least a trend favoring IFN-K is observed on the BICLA response (i.e. the second co-primary endpoint).

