5.3 Statistical/Analytical issues

5.3.1 Adjustments for Covariates

All models ANCOVA, MMRM, Logistic regression) will be adjusted on the minimization factors used for randomization (Ethnic (see section 9 Derived data) Origin, Age group, Presence or absence of renal involvement according to the BILAG at screening, With or without CS treatment at screening, With or without HCQ treatment at screening, With or without MMF treatment at screening).

In addition, MMRM will be adjusted on the baseline value.

For “Ethnic origin”, the reclassified values (see section 9 Derived data) will be used for primary analysis. The values from the eCRF will be used for sensitivity analysis. In the same way, for “Presence or absence of renal BILAG at screening”, the re-computed renal BILAG score derived in the statistics analysis datasets will

Statistical Analysis Plan

Study Name: IFN-K-002

SAP version & date: v4, 18/Jun/2018

be used for primary analysis. The values from the eCRF will be used as sensitivity analysis. (Statistical tables 14.2.3.1.4 & 14.2.3.2.3)

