14.2.3.1.2	Primary efficacy analysis - First co-primary endpoint - Change from baseline					X
14.2.3.1.3	Primary efficacy analysis - First co-primary endpoint - ANCOVA model					X
14.2.3.1.4	Primary efficacy analysis - First co-primary endpoint - ANCOVA model - Covariates as randomized			X		
14.2.3.2.1	Primary efficacy analysis - Second co-primary endpoint - Response at Week 36					X
14.2.3.2.2	Primary efficacy analysis - Second co-primary endpoint - Logistic regression model					X
14.2.3.2.3	Primary efficacy analysis - Second co-primary endpoint - Logistic regression model - Covariates as randomized			X		
14.2.3.3.1	Primary efficacy analysis - First co-primary endpoint - ANCOVA model with status of IFN α neutralizing antibodies (positive/negative) at Week 36 as dependent variable			X		

Statistical Analysis Plan

Study Name: IFN-K-002

SAP version & date: v4, 18/Jun/2018

Number	Title	Screened	SAF	FAS	PP	Other
14.2.3.3.2	Primary efficacy analysis - Second co-primary endpoint - Logistic regression model with status of IFN α neutralizing antibodies (positive/negative) at Week 36 as dependent variable			X		
14.2.4	Sensitivity efficacy analysis - First co-primary endpoint - MMRM			X		
14.2.5.1	Secondary efficacy analysis - SRI-4 response at Week 36			X		
14.2.5.2	Secondary efficacy analysis - SRI-4 response - Logistic regression model			X		
14.2.5.3	Secondary efficacy analysis - SRI-4 response - Logistic regression model with status of IFN α neutralizing antibodies (positive/negative) at Week 36 as dependent variable				X	
14.2.5.4	Secondary efficacy analysis - SRI-4 response at Week 36				X	
14.2.5.5	Secondary efficacy analysis - SRI-4 response - Logistic regression model				X	
14.2.5.6	Secondary efficacy analysis - Composite SRI-4 response (CS 5 mg) at Week 36			X		
14.2.5.7	Secondary efficacy analysis - Composite SRI-4 response (CS 5 mg) - Logistic regression model			X		
14.2.5.8	Secondary efficacy analysis - Composite SRI-4 response (CS 5 mg) - Logistic regression model with status of IFN α neutralizing antibodies (positive/negative) at Week 36 as dependent variable				X	
14.2.5.9	Secondary efficacy analysis - Composite SRI-4 response (CS 7.5 mg) at Week 36			X		
14.2.5.10	Secondary efficacy analysis - Composite SRI-4 response (CS 7.5 mg) - Logistic regression model			X		

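### The SAP models adjust for corticosteroid, HCQ and MMF use at screening, although the trial minimises on, and the protocol model adjusts for, use at randomisation; the change is undeclared and costs a little precision.

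*SAP*

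**What the plan says.** **Allocation.** Protocol 9.2.2 minimises on ethnic origin, age group, renal BILAG and three drug factors: "With or without CS treatment at randomization", "With or without HCQ treatment at randomization" and "With or without MMF treatment at randomization". SAP 2.3.1 repeats this list with the same timing.

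**Protocol model.** Protocol 13.9.2 carries that timing into the primary ANCOVA: "hydroxychloroquine treatment and MMF treatment at randomization - will be included as covariates". The logistic model for BICLA adjusts for the same factors.

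**SAP models.** SAP 5.2.4.1 presents its covariates as the factors used in minimisation, but dates the drugs differently: "corticosteroid treatment, hydroxychloroquine treatment and MMF treatment at screening - will be included as covariates". The BICLA logistic model takes over the same list by reference. SAP 5.2.4.2 does the same for the repeated-measures model. SAP 5.3.1 makes it the rule for every ANCOVA, MMRM and logistic model: "With or without CS treatment at screening, With or without HCQ treatment at screening, With or without MMF treatment at screening".

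**Elsewhere in the SAP.** The demographic summary in SAP 5.2.1 keeps the three drug factors at randomisation. SAP section 7, which lists departures from the protocol, does not mention the timing. SAP 5.3.1 describes a sensitivity analysis on the source of the covariates for ethnic origin and renal BILAG only, although the corresponding tables in SAP 10.1 (14.2.3.1.4 and 14.2.3.2.3) carry a broader title, for example "ANCOVA model - Covariates as randomized".

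**The concern.** The usual principle is to analyse by the factors on which allocation was balanced, with the values used for the balancing. The SAP intends this but attaches a different date to three of the six factors.

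The two dates can give different values. Visit 2 may fall up to 28 days after Visit 1 (protocol 10.9.2). Protocol 7.1 allows for treatment being added after the screening samples: "All relevant samples should be collected before any new SLE related treatment is initiated". Protocol 5.5 speaks of treating active disease with CS and/or permitted immunosuppressants at screening.

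At stake is the precision of both co-primary models and of the SRI models that use the same adjustment. Protocol 5.5 says that CS may affect both the gene signature and the antibody response, so CS status is plausibly prognostic. The gene-signature test also decides whether BICLA is tested at all, so power lost there carries forward.

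**Working it through.** **1. Which factors can change between the two dates**

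| Drug | Prior use required (protocol 8.3.1, Table 4) | New start possible within 28 days before Visit 2? |
|---|---|---|
| HCQ | at least 8 weeks before first dose | No: 8 weeks is longer than 4 |
| MMF | at least 12 weeks before first dose | No: 12 weeks is longer than 4 |
| CS | dose cap only, no minimum duration | Yes |

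A patient can qualify on HCQ, be off CS at Visit 1 and be on CS at Visit 2. Minimisation counts that patient as a CS user; the SAP model counts the same patient as a non-user. Someone who stopped a drug in between would be misclassified the other way.

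**2. The plan's own power figure**

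Inputs (protocol 13.1): difference 32.6, SD 68, 80 per group, two-sided 5%. The exact two-sample t-test gives 85.4% and the normal formula 85.8%. The stated 85% is reproduced.

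**3. Size of the loss, upper scenario**

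Assumptions not in the documents: 70% on CS at randomisation, a CS effect of 1 SD (68 points), 30% of those users having started after screening, and exact balance on CS at randomisation. The protocol's 68 is the SD of the change for an unadjusted test, so it already contains any CS variation; I hold the total at 68.

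- Variance of CS at randomisation: 0.7 × 0.3 = 0.21. On CS at screening: 0.7 × 0.7 = 0.49, variance 0.49 × 0.51 = 0.2499. Covariance: 0.49 − 0.7 × 0.49 = 0.147. Squared correlation: 0.147² / (0.21 × 0.2499) = 0.412.
- Adjusting for CS at randomisation: residual SD = 68 × √(1 − 0.21) = 60.4; SE = 60.4 × √(2/80) = 9.56; power = Φ(32.6/9.56 − 1.96) = Φ(1.45), about 93%.
- Adjusting for CS at screening: the model's residual SD = 68 × √(1 − 0.21 × 0.412) = 65.0, so its SE is 10.28 and the rejection threshold is 1.96 × 10.28 = 20.1. The true spread of the estimate is smaller, because CS at randomisation is balanced. It is √(9.56² + 2.42²) = 9.86, where 2.42 = 40 × 0.061: 40 = 68 × 0.147/0.2499 is the slope on CS at screening, and 0.061 = √(2 × 56 × 0.3 × 0.7/80²) is the chance imbalance in that covariate. Power = Φ((32.6 − 20.1)/9.86) = Φ(1.27), about 90%. Type I error = 2Φ(−20.1/9.86), about 4.1%.
- No CS adjustment: threshold 1.96 × 68 × √(2/80) = 21.1; power = Φ((32.6 − 21.1)/9.56) = Φ(1.20), about 88%.

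Simulation of this scenario gave 92%, 89% and 88%. At 0.5 SD with 10% starters and total SD 68 it gave 87.3% against 87.0%.

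**4. If the CS effect is added on top of SD 68**

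This raises the total SD to 68 × √1.21 = 74.8. The upper scenario then gives 86% as randomised, 82% with screening status and 80% unadjusted, a loss of 4 points. Simulation figures for type I error were 5.0%, 4.3% and 3.0%.

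**5. With the planned minimisation (probability 0.80, six factors)**

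A separate simulation of 160 patients, 2,500 runs per scenario, also added the CS effect (0, 34 or 68 points) to SD 68. It assumed 70% on CS at screening, with 10% or 50% of the rest starting before randomisation (about 5 or 24 patients). Power was 84.4 to 85.5% adjusting at randomisation and 82.6 to 85.2% adjusting at screening; the largest loss was 85.2 − 82.6 = 2.6 points. Type I error was 4.6 to 5.8% against 4.6 to 6.0%, no clear difference at a simulation error of √(0.05 × 0.95/2500) = 0.4 points. With a true difference of 32.6, the mean estimate was close to −32.5 under both adjustments.

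**The case against.** **It may be a labelling slip.** The SAP itself describes these covariates as the minimisation factors and keeps the right timing in SAP 2.3.1 and 5.2.1. That reading is plausible, but the screening date is the written instruction in three SAP sections, including the general rule, so a programmer would follow it. If the date was chosen on purpose, section 7 should say so.

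**A reader might infer that patients are analysed in the wrong group.** The documents do not support that. SAP 3.3.1 analyses the full analysis set by random assignment; only a covariate category can be wrong. Both versions of the covariate are measured before treatment, so no bias in the treatment comparison follows.

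**A reader might infer that all three drug factors go wrong through new starts.** The required prior use of HCQ and MMF exceeds the screening window, so only CS can be newly started within it.

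**The upper scenario is extreme.** This stands. With 70% of 160 on CS (112), 30% starters is about 34 patients, which is 34 of the 82 off CS at screening, or 41%, starting within four weeks. A 1 SD effect has no support in the documents: protocol 5.5 says only that CS may have an impact, and mandatory tapering by Week 24 should weaken baseline CS status as a predictor at Week 36. No starter frequency is given, and CS begun at the screening visit might be recorded as use at screening.

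**The sensitivity tables may already cover the drug factors.** Their title is unrestricted, so this cannot be excluded. But the only description, in SAP 5.3.1, names two factors and not these three.

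**Conclusion.** The mismatch is established by the text: one timing in protocol 9.2.2 and 13.9.2 and SAP 2.3.1 and 5.2.1, another in SAP 5.2.4.1, 5.2.4.2 and 5.3.1, with no declaration in section 7. In practice it concerns patients whose CS status changes between Visit 1 and Visit 2.

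The consequence is modest. The estimate is unbiased, and any effect on type I error is small and in the conservative direction. The power loss is from under 1 to about 4 points for assumed CS effects of 0.5 to 1 SD and 10 to 30% of CS users starting after screening; the top of that range needs the extreme assumptions above. It would be wrong to infer that the trial drops below its planned power: figures of 82% or 80% arise only when the CS effect is added to the stated SD. With the total SD held at 68, power stays at or above the planned 85% in the scenarios examined. This is a free improvement, not a threat to the validity of the primary analysis.

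**What to change.** In SAP 5.2.4.1, 5.2.4.2 and 5.3.1, date the CS, HCQ and MMF covariates at randomisation, and state that the values are those used for minimisation. Apply Tables 14.2.3.1.4 and 14.2.3.2.3 to all six minimisation factors, and say so in SAP 5.3.1.

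The cost is a few words in three sections. The values already exist, because the allocation system needed them, and the change restores the protocol's model. No sample size or power figure in the documents changes. If screening status was intended, SAP section 7 should declare and justify it, and the as-randomised tables should still cover the three drug factors.

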2.3.2 Determination of sample size

The primary objective of this study is to evaluate the neutralization of the IFN gene signature following treatment with IFN-K, as measured by the change from baseline of the expression of IFN-induced genes **and** to evaluate the efficacy of treatment with IFN-K using the British Isles Lupus Assessment Group (BILAG)-based Composite Lupus Assessment (BICLA) response criteria. The following assumptions were made for the sample size calculation:

- The error probability for a 2-sided t-test should not exceed 5%;
- The power should be 80% or higher;
- The change of the expression of IFN-induced genes in patients treated with IFN-K is assumed to be -22.6% (data from study IFN-K-001, Lauwers et al., 2013);
- The change of the expression of IFN-induced genes in patients treated with placebo is assumed to be 10% (data from study IFN-K-001, Lauwers et al., 2013);
- The common standard deviation of the change is 68 (data from study IFN-K-001, Lauwers et al., 2013).

The assumptions for the change in expression of IFN gene signature and the standard deviation are based on the original data of study IFN-K-001 as presented in Lauwers *et al.*, 2013.

With 80 evaluable patients per group i.e. a total of 160 evaluable patients, the study will have a power of 85% to detect a difference of 32.6% in the expression of IFN-induced genes in patients treated with IFN-K compared to patients treated with placebo, assuming that the common standard deviation is 68% and using

Statistical Analysis Plan

Study Name: IFN-K-002

SAP version & date: v4, 18/Jun/2018

a two group t-test with a 0.050 two-sided significance level. Assuming a rate of 10% drop-out patients, 178 patients should be enrolled in order to have 160 evaluable patients at Week 36 (80 evaluable patients in each treatment arm=90% of the enrolled patients).

Assuming a BICLA response of 20.6% in the placebo group and 40.6% in IFN-K treated patients (i.e. an absolute difference of 20%) with 80 evaluable patients per group, there will be a 73% power to detect a difference of 20% in the BICLA response criterion.

The sample size needed to ensure a 80% power to the comparison of BICLA response rates between IFN-K and placebo for different response rates in the placebo arm and varying between groups differences are presented in Figure 2 of the protocol. 97 evaluable patients per group would be needed for a power of 80% to detect a difference of 20% with a placebo response rate of 20.6%.

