4.1 Efficacy endpoints

4.1.1 Primary efficacy endpoint(s)

Two co-primary endpoints are evaluated in the trial:

- Change from baseline in the expression of IFN-induced genes at Week 36.
- Response to treatment with IFN-K as measured by the British Isles Lupus Assessment Group (BILAG)-based Composite Lupus Assessment (BICLA) response criteria at Week 36:
 - All BILAG A scores at baseline improve to B/C/D and all BILAG B scores improve to C/D at Week 36
and
○ No BILAG worsening in other body systems: no new BILAG A or ≥ 2 new BILAG B scores at Week 36
and
○ No worsening in SLEDAI-2K total score at Week 36 compared with baseline
and
○ No deterioration in PGA (< 10% worsening) on VAS 100 mm at Week 36 compared with baseline
and
○ No addition or increased dose level of anti-malarial drugs or immunosuppressive drugs or corticosteroids between Week 24 and Week 36 (this criterion will be identified by medical review)

Statistical Analysis Plan

Study Name: IFN-K-002

SAP version & date: v4, 18/Jun/2018

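### The BICLA logistic model omits Week 0 disease activity; adding the number of baseline BILAG A/B systems would probably gain a little precision

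*SAP*

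**What the plan says.** SAP 5.2.4.1 fits a logistic regression for BICLA response at Week 36 with treatment as the explanatory variable, "while adjusting for the minimization factors used for randomization, as listed for the analysis of the first primary end-point". That list is ethnic origin, age group, renal involvement at screening, and use of corticosteroids, hydroxychloroquine and MMF. SAP 5.3.1 and protocol 13.9.2 give the same set. SAP 5.3.1 adds the baseline value to the MMRM only.

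The first BICLA component in SAP 4.1.1 reads "All BILAG A scores at baseline improve to B/C/D and all BILAG B scores improve to C/D at Week 36". SAP 5.4.1 fixes Week 0 as the BILAG baseline for each body system, so the number of A or B systems can be derived. SAP 5.2.1 already tabulates baseline activity by arm: "Efficacy variable at baseline (IFN score, SLEDAI-2K score, BILAG global score".

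On power, SAP 2.3.2 starts from these rates: "Assuming a BICLA response of 20.6% in the placebo group and 40.6% in IFN-K treated patients". For an analysed sample of 80 in each arm, its conclusion is that "there will be a 73% power to detect a difference of 20% in the BICLA response criterion". BICLA is tested only after the gene-signature endpoint succeeds, and then it "will be tested also at an error probability of 5% for a 2-sided test". For the study to be called positive, SAP 5.2.4.1 asks only for a trend on BICLA. It labels an observed difference of 10% marginal and 15% important, regardless of significance.

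**The concern.** Each further system graded A or B at Week 0 adds a condition that a responder must meet. Entry (protocol 8.3.1) requires at least one A and/or at least two B grades. The only upper limits are the exclusions for renal A and neuropsychiatric A (protocol 8.3.2), so the count can vary between patients. Minimisation does not balance it. The one disease-related covariate, renal involvement, covers a single system and is taken at screening.

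If the count does predict response, leaving it out keeps explainable variation in the comparison. Chance differences in the count between arms then add noise to the BICLA result. The sponsor acknowledges that this endpoint falls short of the protocol's 80% power target, and SAP 5.2.4.1 reads it partly on the size of the observed difference.

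**Working it through.** **Inputs from the documents.** BICLA rates 20.6% and 40.6%, 80 per group, two-sided 5% (SAP 2.3.2, 5.2.4.1). **Assumed, because the documents give neither:** the distribution of the number *k* of A/B systems at Week 0, and its association with response.

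**1. The stated 73%.** For two proportions with pooled null variance, the mean rate is 0.306.
- Null SE = √(2 × 0.306 × 0.694 / 80) = 0.0729. Alternative SE = √((0.206 × 0.794 + 0.406 × 0.594) / 80) = 0.0711.
- Power = Φ((0.200 − 1.96 × 0.0729) / 0.0711) = Φ(0.804) = 78.9%. This is not 73%.
- With a continuity correction, the effective n is 80 × (1 − 1/(80 × 0.2))² = 70.3, and power is 73.5%. Fisher's exact test gives 74.1%.

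So 73% reproduces as a corrected or exact unadjusted figure.

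**2. Power of the planned model.** In simulations with treatment and stand-ins for the six minimisation factors (Wald test, 3,000 trials per scenario, Monte Carlo SE about 0.7 points), power at 80 per arm was 76.9% to 80.2%, typically 78-79%. This is the right starting point.

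**3. Effect of the count if systems improve independently.** Assume 15/45/28/12% of patients have 1/2/3/4 active systems, and P(response) = p^k. Matching the overall rates gives p = 0.471 on placebo and 0.666 on IFN-K. For example, on placebo, 0.15 × 0.471 + 0.45 × 0.222 + 0.28 × 0.104 + 0.12 × 0.049 = 0.206. From 1 to 4 systems, response falls from 47% to 5% on placebo and from 67% to 20% on IFN-K. Adding k raised simulated power from 78.7% to 82.1%, a gain of 3.4 points.

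**4. Check by variance.** Under step 3, the between-k variance of response probability is 0.0165 on placebo and 0.0195 on IFN-K.
- Variance of the risk difference due to k: (0.0165 + 0.0195) / 80 = 0.00045, an SD of 2.1 points.
- Total variance: 0.0711² = 0.00506, an SD of 7.1 points. The share due to k is 0.00045 / 0.00506 = 8.9%.
- Removing that share is worth 80 / (1 − 0.089) ≈ 88 per group. By the pooled formula, 85 per group gives 81.3% and 89 gives 83.1%, against 78.9% at 80. This agrees with step 3.

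**5. Range.** Independence is the favourable case. If improvement is correlated within a patient, the gain shrinks (points of power, 80 per arm; two sets of runs):

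| Within-patient correlation | 1-4 systems (15/45/28/12%) | 1-3 systems (20/60/20%) |
|---|---|---|
| 0 | +3.0 and +3.4 | +2.8 and +2.7 |
| 0.3 | +2.3 | +1.3 |
| 0.5 | +1.6 | +1.2 |
| 0.7 | +0.7 and about +0.6 | +0.7 and about +0.8 |

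As an alternative, assume a fixed odds ratio per extra system, with narrow (1-3 systems, 20/60/20%), middle (1-4, 25/45/20/10%) and wide (1-5, 30/30/20/10/10%) distributions:

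| Odds ratio per system | Narrow | Middle | Wide |
|---|---|---|---|
| 1 | none | none | none |
| 0.7 | +0.4 | +1.2 | +1.4 |
| 0.5 | +0.7 | +2.3 | +4.0 |
| 0.35 | +2.9 | +5.3 | +6.3 |

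**6. Validity.** Simulated type I error without and with the count was 5.1% and 5.4% in one set (Monte Carlo error about 0.4 points). In another, with 4,000 trials and all six factors, it was 5.7% and 6.0%. The omission does not inflate the error rate.

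**7. Model size.** Ethnic origin uses up to 3 terms, the five binary factors 5, and treatment 1: up to 9. Expected responders are 80 × 0.206 + 80 × 0.406 = 16.5 + 32.5 = 49, so responders per term fall from 49/9 = 5.4 to 49/10 = 4.9.

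**The case against.** The strongest defence is that nothing here is an error. The SAP fits the model the protocol specified and adjusts for the factors used in allocation, and its test is valid. That stands. A reader might infer that an imbalance in active systems would bias the treatment estimate. Under randomisation such an imbalance is sampling variation, already covered by the standard error and the 5% level.

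A reader might also infer that the count strongly predicts response. The documents contain no such figure. Entry may keep the count within a narrow range. A common drug effect and a common steroid taper may make systems improve together. The SLEDAI-2K, PGA and medication components need not follow the count. Nor does a count separate an A, which need only reach B, from a B, which must reach C or D. These points reduce the expected gain; only a complete lack of association removes it.

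A third tempting inference is that adjustment would lift power from 73% to above 80%. It would not, because the two figures come from different tests.

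Finally, BICLA is judged on a trend, and the 10% and 15% labels apply to an observed difference that a covariate in an odds-ratio model leaves unchanged. This is correct, but it does not make precision irrelevant. Under step 3, chance imbalance in the count alone moves the observed difference by about ±4 points (1.96 × 2.1), while the two thresholds lie 5 points apart. A standardised risk difference from the adjusted model addresses this.

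**Conclusion.** The concern holds as a matter of precision. The BICLA model has no Week 0 activity covariate, although the endpoint's definition makes the number of active systems a likely predictor. At 80 per arm, adding the count would raise power from about 78-79% by roughly 0.5 to 3.5 points for 1 to 4 active systems, depending on within-patient correlation. The gain reaches about 6 points under stronger assumed associations and is zero if there is none. All these gains rest on assumed distributions and associations. The documents do not support a claim of bias, an invalid test, a demonstrated strong predictor, or a change in the study's success rule. The change is worth making because the data are already collected and the cost is small.

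**What to change.** Before database lock and unblinding, amend SAP 5.2.4.1 and 5.3.1 as follows.

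- Add one covariate to the BICLA logistic regression: the number of BILAG systems graded A or B at Week 0. Specify the count itself and leave no choice between it and the BILAG global score. The score gives an A more weight than a B (12 against 8, SAP 5.2.4.3.3), although the B has to reach a lower grade to count as improved.
- Keep the model with minimisation factors only as a sensitivity analysis.
- Beside the odds ratio, report the standardised (marginal) risk difference from the adjusted model, so that the result can be read against the 10% and 15% thresholds.

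The cost is one more parameter in a model with up to nine non-intercept terms and about 49 expected responders, and an odds ratio that is conditional on the count. No new data are needed. SAP 3.3.2 allows for missing baseline BILAG, but where all of it is missing, BICLA cannot be scored in any case.
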